10.1 STUDY MONITORING, AUDITING, AND INSPECTING	21
10.2 AUDITING AND INSPECTING	22

[name] IND, Topical Composition for Cutaneous Mastocytosis

11 ETHICAL CONSIDERATIONS	22
12 STUDY FINANCES	22
12.1 FUNDING SOURCE	22
13 PUBLICATION PLAN	22
14 REFERENCES	23
15 ATTACHMENTS	24

Study Summary

Title	AN OPEN-LABEL PILOT STUDY TO EVALUATE THE
	EFFECTIVENESS AND TOLERABILITY OF A TOPICAL
	COMPOSITION THERAPY FOR THE TREATMENT OF
	CUTANEOUS MASTOCYTOSIS
Running Title	Topical Composition for Cutaneous Mastocytosis
Protocol Number	Pending
Phase	Phase II Feasibility/Proof of Concept
Methodology	Open Label
Subject participation	Two weeks
Duration	
Study Duration	One year
Single or Multi-Site	Single Center
Objectives	To determine the effectiveness and tolerability of a novel topical
	preparation for the treatment of cutaneous lesions of mastocytosis.
Number of Subjects	10
Diagnosis and Main	Cutaneous mastocytosis
Inclusion Criteria	
Study Product,	Topical composition 'Skin Guard' applied twice daily for four weeks.
Dose, Route,	
Regimen	
Duration of	2weeks
Administration	

1 Introduction

This human clinical research study will be carried out in accordance with the protocol, applicable United States government regulations and Mayo Clinic research policies and procedures.

1.1 Background

Condition to be studied

Mastocytosis is a rare disorder of clonal mast cell proliferation. There are several subclasses of systemic mastocytosis (SM) ranging from indolent disease to aggressive disease, mast cell leukemia and mast cell sarcoma. The major criterion for defining systemic disease is the presence of mast cell (MC) infiltration of organs (commonly assessed by tissue or bone marrow biopsy). Patients with SM may or may not have cutaneous involvement. Whereas in cutaneous mastocytosis (CM), MC infiltration is limited to the skin.

Why the investigational product may be beneficial

Topical treatment of symptoms resulting from cutaneous involvement by mastocytosis (pruritus, flushing, urticaria, angioedema) is mainly limited to topical lubricants, topical corticosteroids, and topical antihistamines, medications that have individually been available for decades. In our own experience, topical cromolyn sodium 0.25% (children), and 1% or 5% (adults) can also be effective for relief of dermal symptoms.

Excessive application of topical steroids can cause skin atrophy or delayed healing, while excessive absorption of topical antihistamines could lead to systemic side effects such as somnolence, dyskinetic symptoms, impairment of performance skills, anticholinergic symptoms and others.

The product to be used will not contain corticosteroids and will use a lower concentration of diphenhydramine (1% vs 2%) than is currently available in over the counter preparations. By combining 3 ingredients, diphenhydramine, cromolyn sodium and trolamine we will leverage the different effects of various classes of medications to block mast cell mediator release (cromolyn sodium), to block mediator (histamine) receptors (diphenhydramine) and to inhibit production of prostaglandin D2 by topical cyclooxygenase blockade (trolamine salicylate).

Pathophysiology relevant to potential study treatment action

Symptoms from mastocytosis result from accumulation of these cells as well as local and remote effects of MC mediators. Mast cells are dynamos for the production of mediators that in the skin can stimulate symptoms by their effects on blood vessel constriction, vasopermeability, and excitation of nerve endings causing itching, hiving, swelling and flushing. The synergistic effect of targeting 3 of the most prevalent (and measurable) mediators should have a beneficial effect on dermatologic symptoms and will allow a lower

concentration (1% vs 2%) of diphenhydramine to be used than is commonly employed in OTC topical preparations of this medication.

Description of the population to be studied

Involvement of the skin in mastocytosis is equally common in men and women. Patients age 18 and above with CM or skin involvement in SM confirmed by skin biopsy who have bothersome, symptoms not controlled with topical and systemic medications will be eligible to participate in this study. Ten patients will be enrolled. Women who are pregnant or nursing will be excluded.

1.2 Investigational Agents

The proposed study refers to a topical composition of the following agents, each of which is currently approved for and is used in clinical practice:

DIPHENHYDRAMINE

Drug Class:H1 antihistamine

Mechanism of Action Diphenhydramine acts as an antihistamine by competing with histamine for receptor sites on effector cells such as mast cells and basophils.

Pharmacology Diphenhydramine is a first generation antihistamine of the ethanolamine class. It has antimuscarinic, antiemetic and sedative effects and competitively antagonizes the effect of histamine on histamine receptors in the GI tract, uterus, large blood vessels, and bronchial muscle. It has multiple other uses such as treating drug-induced extrapyramidal effects, vertigo and Meniere's disease. Diphenhydramine is metabolized in the liver and the total body clearance of orally administered diphenhydramine is 11.7 to 49.2 mL/min/kg.

TROLAMINE SALICYLATE

Drug Class: Non-steroidal anti-inflammatory

Mechanism of Action: The active moiety in trolamine salicylate is salicylic acid which, by inhibition of prostaglandin synthesis inhibits pain, inflammation and hyperemia. The downstream effect of inhibition COX-1 includes blocking synthesis of prostaglandin (PG) D2, a product of mast cells.

Pharmacology: Available as an over-the-counter preparation, 10% topical trolamine salicylate is commonly used to treat musculoskeletal pain and osteoarthritis.

CROMOLYN SODIUM (disodium cromoglycate)

Drug Class: Anti inflammatory agent and mast cell stabilizer.

Mechanism of Action: Cromolyn sodium blocks the release of histamine and SRS-A (slow-reacting substance of anaphylaxis) from sensitized mast cells.

Pharmacology: Cromolyn sodium is available in multiple dosage forms including an oral form used for treating gastrointestinal disorders in hypereosinophilic disorders and in mastocytosis; ophthalmic drops for treating allergic conjunctivitis; a nasal spray for treating allergic rhinitis; an inhalant solution for treating asthma, and is prepared in a compounded topical cream for treatment of cutaneous mastocytosis. Oral cromolyn sodium is poorly absorbed and the bioavailability of inhaled (8%), ophthalmic (0.03%), and oral (not more than 1%) is low. In one study of the absorption of oral [14C] disodium cromoglycate only 0.4% of an oral dose (20 mg) appeared in the 24 hr urine sample and 83% was recovered from the feces. While intravenous administration resulted in approximately equal amounts (30-50%) being excreted via the urine and feces (Walker SR, Evans ME, Richards AJ, Paterson JW. The fate of [14C] disodium cromoglycate in man. J. Pharm. Pharmac. 1972; 24: 525-531)

VANICREAM (OTC)

Drug Class: Moisturizer; Vehicle for topical preparations

Mechanism of Action: Vanicream is used as a topical lubricant that does not clog pores and is not absorbed. It is used by itself as a moisturizer and for compounding of topically applied skin care products.

Pharmacology: Vanicream is formulated as an OTC preparation comprised of: purified water, white petrolatum, sorbitol solution, cetearyl alcohol, propylene glycol, ceteareth-20, simethicone, glyceryl monostearate, polyethylene glycol monostearate, sorbic acid, BHT. It is free of lanolin, fragrances, parabens and formaldehyde. Vanicream is compatible with numerous topical agents used for skin care.

2 Study Objectives

The primary objective of this study is to assess the effectiveness of twice daily application of trolamine salicylate 10%, sodium cromolyn 5%, and diphenhydramine 1% on symptoms resulting from cutaneous mastocytosis.

3 Study Design

3.1 General design

This is a phase II nonrandomized, open-label pilot study of the effectiveness and tolerability of a novel composition comprised of daily application of trolamine salicylate 10%, sodium cromolyn 5%, and diphenhydramine 1% in vanicream on skin producing cutaneous symptoms of mastocytosis. Subjects will be screened by the Department of Allergic Diseases at the Mayo Clinic in Rochester MN and interested qualified subjects will be consented and offered participation. The study is designed to establish

feasibility/proof of concept and will not include randomization or crossover components. Please see Section 6: Study procedures for a detailed description.

3.2 Primary Study Endpoints

Scorma Index[see below]

The proportion of participants who achieved complete resolution or near-complete clearing of cutaneous symptoms of treated, involved skin after 2 weeks' treatment will be evaluated using the SCORing MAstocytosis (SCORMA) index. SCORMA has been utilized to evaluate the severity of cutaneous mastocytosis and to correlate with serum tryptase levels. Repeated SCORMA determinations can "provide a rapid impression of changes in the clinical status" in mastocytosis (HeideR, van Doorn K, Mulder PG et al. Serum tryptase and SCORMA (SCORing MAstocytosis) index as disease severity parameters in childhood and adult cutaneous mastocytosis. Clinical and Experimental Dermatology 2008; 34: 462-468.)

The SCORMA index is calculated by the formula A/5 +5B +2C/5 where A=Extent of skin involvement,

B= Intensity (pigmentation/erythema + vesiculation + elevation + positive Darier's sign each rated 0[absent], 1[mild] 2[moderate] or 3[severe]).

C= subjective symptoms utilizing visual analog scale 1-10 of the following: provoking factor(s), flushing, diarrhea, pruritus, localized bone pain.

Since it will be impractical for patients to apply Skin Guard to the entire body surface area, and not all areas of the skin will be involved to the same extent, we will limit application to between 9% and 18% of the skin (see SCORMA figure). In this regard we will attempt, when possible, to utilize equally involved sides of the torso or extremities to facilitate evaluation of effectiveness. We will generate not only a "Global" SCORMA value, but in addition a SCORMA value for the treated, involved skin. The latter should give a more accurate estimation of the effectiveness on treated areas.

Quality of Life –SkinDex-16[see below]. Skindex-16, a validated measurement of the effects of skin diseases on patients' quality of life will be utilized to follow this parameter. SkinDex has been used and adapted for dermatologic research internationally (Chren M-M, The SkinDex instruments to measure the effects of skin disease on quality of life. Dermatology Clinics 2012; 30: 231-236).

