We will use the SCORMA index and SkinDex-16 as both continuous variables and categorical variables. Change in SCORMA and of SkinDex-16 from baseline to the 2week follow-up visit will be estimated using sample mean, median, standard deviation, interquartile range, and range. SCORMA and SkinDex-16 will be compared from baseline to the follow-up time point using a paired Wilcoxon signed rank test.

Interim Analysis

There will not be any interim analysis given the low risk profile of the study formulation.

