- •No current use of Interferon Alpha; Cladribine; Imatinib Mesylate; Midostaurin; Avapritinib, Prednisone or other chemotherapy agents.
- •No current use of chemotherapeutic agents
- •Good general health as confirmed by medical history
- •Female patients of childbearing potential with a negative urine pregnancy test who agree to use effective methods of birth control or remain abstinent during treatment
- Patients who are willing and capable of cooperating to the extent and degree required by the protocol
- Patients who read and sign an approved informed consent for this study

The study includes 2 visits over 2weeks. There will be no cost to participate. You will not be compensated for your time.

Who can I contact for more information?

Principal Investigator:	[contact]
[name].	
	Email:
	[contact]
	Address:
	[name]
	[name]
	[name]

Primary Safety Endpoints Table

Patient Name:

[figure not shown]
Symptom (Patient/Physician)	Week→	
	0	2
itching		
swelling		
stinging/burning		
dryness		

none (0), mild (1), moderate (2), or severe (3)

SCORMA INDEX Name of patient Institution Date of birth Physician Date of visit Patient number (8.5)Between brackets: Age under 2 yrs. A: Extent please indicate the area involved [] B: Intensity average representative area Criteria Intensity Intensity items Pigmentation / erythema 0 = absent Vesiculation 1 = mild Elevation 2 = moderate Positive Darier's sign 3 = severe C: Subjective Symptoms Visual Analog Scale (by parents if child < 5 years) 1. Provoking Factor(s) 0 ------ 10 2. Flushing 0 ------ 10 3. Diarrhea 0 ------ 10 Pruritus Localized Bone Pain

[]

Scorma index: A/5 + 5B + 2C/5

LOCAL SCORMA INDEX-FOR AREA(S) TREATED-Indicate Area(s) Treated

of skin treated-INDICATE A	AREA(S) TREATED
Intensity	Intensity Items
[]	0= Absent
	1= Mild
	2= Moderate
	3= Severe
is	
Visual Analog Scale	
0	10
0	- 0
0	10
0	10
0	10
5 + 5B + 2C/5	
	Intensity [] [] [] [] ss Visual Analog Scale 0 0 0 0 0 0

Page 28 of 32 [name]

Clinical Response Assessment: Global SCORMA Assessment

Week	SCORMA	% Resolution	ASSESSMENT			
0						
2						

Complete response:

Clinically significant SCORMA improvement in all 3 parameters of % skin involvement; activity or symptoms &/or

Resolution of 75% of cutaneous lesions

Near Complete response:

Clinically significant SCORMA improvement in two of 3 parameters of % skin involvement; activity or symptoms and/or

Resolution of >50% of cutaneous lesions

Partial Response:

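### The primary objective is symptom relief, but no planned effectiveness analysis isolates symptoms, and the SCORMA total that is tested gives them at most 20 of 100 points (pruritus 4)

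*Combined protocol and SAP*

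**What the plan says.** **Objective.** Section 2 makes the primary objective the effect of twice-daily application "on symptoms resulting from cutaneous mastocytosis". Section 1.1 names the symptoms (pruritus, flushing, urticaria, angioedema) and rests the rationale on blocking the mediators behind them. The Study Summary instead describes a "preparation for the treatment of cutaneous lesions of mastocytosis", and the Primary Hypothesis in section 7.2.1 also speaks of lesions.

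**Measure.** Section 3.2: "The SCORMA index is calculated by the formula A/5 +5B +2C/5". A is extent. B adds four signs graded 0-3 (pigmentation/erythema, vesiculation, elevation, Darier's sign). For C the text reads "C= subjective symptoms utilizing visual analog scale 1-10 of the following", followed by provoking factors, flushing, diarrhea, pruritus and bone pain. The SCORMA form in the attachments prints the scale differently: "1. Provoking Factor(s) 0 ------ 10". SkinDex-16 is also listed in section 3.2.

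**Analysis.** Section 7.2.1: "We will use the SCORMA index and SkinDex-16 as both continuous variables and categorical variables". Change to week 2 is summarised and tested by a paired Wilcoxon signed rank test. The primary hypothesis is judged by the proportion with complete or near-complete response, built from three SCORMA parameters, three SkinDex-16 domains and percentage lesion resolution. Itching has a separate analysis only as a 0-3 tolerability rating (section 3.4), reported as proportions under safety.

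**The concern.** The objective concerns symptoms, while the continuous SCORMA test uses a total weighted towards visible signs. A fall in that total may come from one-grade shifts in signs. A real reduction in itch may be hard to see against grading noise in those signs.

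The responder rule does not fill the gap, because symptoms are only one of its three SCORMA parameters and one of its three SkinDex domains. Section 7.1 says the pilot should give a preliminary efficacy estimate for designing a larger study. As planned, it would give no stated effectiveness estimate for symptoms taken alone.

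**Working it through.** The plan states no power figure and no SCORMA maximum, so there is no figure of its own to reproduce.

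**1. Weights.** The formula and the four 0-3 signs come from section 3.2, and the 0-10 scales from the form. Assumed: A runs 0-100 and C is a sum.

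- Extent: 100/5 = 20
- Intensity: 5 × (4 × 3) = 60
- Symptoms: 2 × (5 × 10)/5 = 20
- Maximum: 20 + 60 + 20 = 100
- Pruritus from 10 to 0: 2 × 10/5 = 4 points
- One grade on one sign: 5 × 1 = 5 points

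**2. Sensitivity to the assumptions.**

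- Local index with A entered as the treated 9-18% of skin: the maximum is 9/5 + 60 + 20 = 81.8 to 18/5 + 60 + 20 = 83.6. Pruritus is then 4.8-4.9% of it.
- Scales on 1-10: the largest pruritus change is 2 × 9/5 = 3.6 points, and a symptom-free patient scores 2 × 5/5 = 2.
- B as a mean, contrary to the plus signs in section 3.2: the maximum is 20 + 15 + 20 = 55 and pruritus is 7.3% of it. One grade on one sign would then be 5/4 = 1.25 points, and the comparison with pruritus would reverse.

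**3. Responder rule.** Take a patient whose symptom parameter and SkinDex Symptoms domain improve and nothing else does. That is one of three SCORMA parameters and one of three SkinDex domains. Both are the partial-response level, whichever way the and/or links are read. The primary hypothesis counts only complete and near-complete response.

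**4. Illustration.** The documents give no SDs, so every value here is assumed: n = 10; two-sided 0.05; pruritus change mean -5, SD 2.5; the other four scales mean 0, SD 1; extent unchanged; each sign shifts one grade up or down with probability p each way; all independent.

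Mean change in the total is 0.4 × 5 = 2.0 points. Its variance is 25 × 4 × 2p + 0.16 × (6.25 + 4) = 200p + 1.64. The last column is simulated.

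| p | SD of total | Mean/SD | Wilcoxon detects, total |
|---|---|---|---|
| 0 | 1.28 | 1.56 | about 99% |
| 0.02 | 2.37 | 0.84 | about 68% |
| 0.05 | 3.41 | 0.59 | about 43% |
| 0.10 | 4.65 | 0.43 | about 24% |
| 0.15 | 5.62 | 0.36 | about 17% |

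The pruritus scale alone has mean/SD = 5/2.5 = 2.0 and is detected in over 99% of trials. Part C alone is equivalent to the p = 0 row (about 99%), because with extent and signs constant the total is part C rescaled.

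For a mean pruritus fall of 3, the total detects it in about 9-23% of trials for p = 0.05-0.15, against about 90% for the pruritus scale.

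If one sign also improves a grade in half the patients, the mean fall in the total becomes 2.0 + 5 × 0.5 = 4.5 points. The total then detects the effect in about 50-83% of trials for p = 0.05-0.15.

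**The case against.** The strongest reply is that the weights do not touch the primary endpoint. The responder rule counts three SCORMA parameters without the factors 5 and 2/5, so symptoms are one of three there, not 20 points in 100. SkinDex-16 is also a listed primary endpoint, tested by the same method, and its first four items ask about itching, burning or stinging, hurting and irritation. This stands. A reader might infer that symptoms go unmeasured or that the objective cannot be answered, and the documents do not support that. What remains is that neither route reports symptoms alone. Section 7.2.1 does not say that the Symptoms domain is tested separately, and itching is one of 16 items.

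A second reply is that the illustration supposes an effect on itch and on nothing else. Section 1.1 expects effects on hiving, swelling and flushing, and B includes erythema, elevation and Darier's sign. This also stands, so the 17-43% range is an unfavourable scenario and not a forecast. A small but uniform fall can reach significance: if all ten patients fall, the exact two-sided p is 2 × (1/2)^10 = 0.002. It would be wrong to conclude that the trial will miss a symptom effect.

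Third, the objective is wider than itch, so pruritus should not be the only symptom outcome. That is accepted.

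Fourth, a reader might think that the 1-10 scale biases the results. It does not bias change from baseline, because a constant floor cancels and no response category requires a score of zero. The text and the form still disagree.

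Last, this is a ten-patient pilot without a power claim. That limits the weight of the point, but a pilot meant to inform a larger trial needs an estimate for its stated objective.

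**Conclusion.** The point holds as a gap between objective and analysis. Under the stated assumptions on A, B and C, symptoms are at most 20% of the tested SCORMA total and pruritus 4%, less than one grade on one sign. No effectiveness analysis isolates symptoms, and relief limited to them cannot count as success under the primary hypothesis.

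The cost in sensitivity depends on how noisily the signs are graded and on whether the signs also improve. In the illustration it runs from almost none (about 99% detection without noise) to severe (about 17%). The documents give no data to place the trial in that range. The objective is measured in part, but without a dedicated estimate.

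**What to change.** In sections 3.2 and 7, pre-specify the change from week 0 to week 2 in four separate effectiveness outcomes for the symptom objective:

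- SCORMA part C
- the pruritus scale
- the flushing scale
- the SkinDex-16 Symptoms domain

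Use the descriptive statistics and signed rank test already planned. Report SCORMA parts A and B separately. Keep the SCORMA total and the responder proportion.

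Reconcile the symptom wording of section 2 with the lesion wording of the Study Summary and the Primary Hypothesis. Align the scale range in section 3.2 (1-10) with the form (0-10).

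The cost is a few lines of text, since every item is already collected at both visits. The downside is a few more unadjusted comparisons in a pilot that already declares no multiplicity adjustment.

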3.4 Primary Safety Endpoints

Minimal systemic absorption is expected with each of the active components. Safety endpoints to be measured at the initial and final visits and include Investigator and Participant observation of local skin tolerability including ratings of itching, swelling

stinging/ burning, and dryness on separate scales as none (0), mild (1), moderate (2), or severe (3).

4 Subject Selection Enrollment and Withdrawal

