6.5 Visit 2-Final visit (Week 2 +/- 1 day)

- a) Reassess cutaneous mastocytosis severity by (Global & Local) SCORMA Indexes; monitor vital signs
- b) Investigator Assessment of Global Improvement
- c) Quality of life assessment:SkinDex-16
- d) Review changes to medical history and current medications
- e) Review contraception (female patients of childbearing potential)
- f) Review adverse events
- g) Review compliance

- h) Repeat photographs
- i) Obtain levels of serum tryptase, urinary N-MH, LTE4, and 2,3 dinor 11β PGF2α
- j) Reconcile study formulation

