7.1 Sample Size determination

Due to the pilot nature of the study, no formal statistical power/sample size calculations are necessary. The sample size of 10 patients will be sufficient for this pilot study to obtain a preliminary estimate of treatment efficacy and to generate data that will be useful in the design of a larger study.

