7.2.1 Definition of response

Complete response:

Clinically significant SCORMA improvement in all 3 parameters of treated, involved skin: % skin involvement; activity or symptoms &/or

Improvement in all 3 SkinDex-16 domains (Emotions, symptoms, functioning) &/or Resolution of 75% of cutaneous lesions

Near Complete response:

Clinically significant SCORMA improvement in two of 3 parameters of treated, involved skin: % skin involvement; activity or symptoms and/or

Improvement in 2 SkinDex-16 domains (Emotions, symptoms, functioning) &/or Resolution of >50% of cutaneous lesions

Partial Response:

Clinically significant SCORMA improvement in one 3 parameters of treated, involved skin: % skin involvement; activity or symptoms and/or

Improvement in 1 SkinDex-16 domain (Emotions, symptoms, or functioning) &/or Resolution of >25% of cutaneous lesions

No response:

No significant SCORMA improvement in any of 3 parameters of treated, involved skin: % skin involvement; activity or symptoms and/or

Improvement in no SkinDex-16 domain (Emotions, symptoms, functioning) &/or Resolution of no cutaneous lesions.

*Additionally, for primary safety endpoints which will be scored as none, mild, moderate, or severe, the proportion of patients in each category at each follow-up time point will be estimated for each of the different safety endpoints. P-values of 0.05 or lower will be considered as statistically significant.

Handling of missing data

This is a prospective study and therefore we do not anticipate any missing data. In the event of any unexpected missing data, no attempt to impute this missing data will be made; missing data will simply be treated as missing in the statistical analysis.

Multiplicity

Since this is an exploratory pilot study, no adjustment for multiple testing is needed. P-value of 0.05 or lower will be considered as statistically significant.

Primary Hypothesis:

The study seeks to demonstrate the effectiveness and tolerability of a novel topical composition consisting of 3 components (diphenhydramine, aspirin and cromolyn sodium) in a neutral skin moisturizing cream (Vanicream) for the treatment of cutaneous lesions of mastocytosis. This will be determined by the proportion of participants who achieve complete or near-complete response utilizing the SCORMA Index, and SkinDex-16 QOL.

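### Section 3.2 seeks equally involved sides to help judge effectiveness, but no visit step, form or analysis scores a matched untreated area or compares sides

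*Combined protocol and SAP*

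**What the plan says.** Section 3.2 explains that treating the whole body is impractical and confines application to 9–18% of the skin. In that connection it states: "we will attempt, when possible, to utilize equally involved sides of the torso or extremities to facilitate evaluation of effectiveness". The same paragraph then defines two scores, a Global SCORMA and a SCORMA for the treated, involved skin.

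The rest of the plan follows those two scores:

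- Section 6.1(a) generates Global and Local values at baseline, and Section 6.5(a) repeats them: "Reassess cutaneous mastocytosis severity by (Global & Local) SCORMA Indexes".
- The attached local form is headed "LOCAL SCORMA INDEX-FOR AREA(S) TREATED-Indicate Area(s) Treated".
- Section 7.2.1 grades response on treated, involved skin, with SkinDex-16 domains and lesion resolution as further or alternative routes.
- The only effectiveness test is in Section 7.2.1: "SCORMA and SkinDex-16 will be compared from baseline to the follow-up time point using a paired Wilcoxon signed rank test". It does not say whether SCORMA here means Global or Local.

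The application instruction in Section 5.2 is directed at symptomatic areas. It mentions neither the 9–18% limit nor an area to be left out. Section 3.1 declares a nonrandomized, open-label pilot without randomization or crossover. Section 3.4 adds: "Minimal systemic absorption is expected with each of the active components".

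**The concern.** Equal involvement of two sides helps in judging effectiveness mainly if the sides are later compared. If both are treated, little is gained from their being alike. The sentence in Section 3.2 therefore points to a within-patient comparison, but no measurement or analysis delivers one.

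What is left is a before-after contrast with one baseline, one follow-up visit at Week 2, no run-in and no control. Section 1.1 describes patients whose symptoms are bothersome and not controlled by existing treatment, so some regression to the mean is possible. Lesions and symptoms may also fluctuate, and exposure to triggers may change. Section 5.3 restricts concomitant topical products and Section 4.2 lists only certain systemic drugs, so other systemic medication may change; Section 6.5(d) reviews such changes. All of these can act on both sides of the body, and the planned analysis would count them towards the cream. Effectiveness is the primary objective (Section 2), and Section 7.1 wants a preliminary efficacy estimate to help design a larger study. An estimate that includes an unknown drift is a weak basis for that.

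**Working it through.** **1. Is a matched untreated area scored anywhere?**

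| Place | What is scored or compared |
|---|---|
| 3.2 | Global; treated, involved skin |
| 6.1(a), 6.5(a) | Global and Local |
| Attached SCORMA forms | whole body; treated areas |
| 7.2.1, response | treated, involved skin; SkinDex-16; lesion resolution |
| 7.2.1, test | baseline versus Week 2 |

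No row contains an untreated area or a comparison of sides. The untreated score cannot be recovered by subtracting Local from Global, because the Global form rates intensity once, on a site taken as typical, and not by area.

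**2. Can SCORMA be rated by side?** The index is A/5 + 5B + 2C/5. Its maxima are:

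- A: 100/5 = 20.
- B: four items scored 0–3, so 5 × 12 = 60.
- C: five scales to 10, so 2 × 50/5 = 20.

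Extent (A) and intensity (B) can be rated for one area. If A is percent of body surface, 9–18% treated gives at most 9/5 = 1.8 to 18/5 = 3.6 points, so B would dominate. In C, only pruritus is readily specific to an area. Provoking factors, flushing, diarrhea and bone pain describe the whole patient and would mostly cancel in a side comparison.

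**3. The planned test at n = 10.** The plan has no power figure to reproduce: Section 7.1 says "no formal statistical power/sample size calculations are necessary". It gives n = 10, and Section 7.2.1 gives the threshold: "P-value of 0.05 or lower will be considered as statistically significant". Two-sided testing is assumed. Of the 2^10 = 1,024 sign patterns, 25 give W+ ≤ 8. The exact size of the rule min(W+, W−) ≤ 8 is therefore 2 × 25/1,024 = 0.0488. The test is sound for the question of whether anything changed over time.

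**4. What a common drift does.** The assumptions, none from the documents, are normal changes with SD 1 on each side, no cream effect, the same mean drift d on both sides, all 10 patients matched, and between-side correlation ρ of 0.5 or 0.8. For each side, change = d + shared part (variance ρ) + own part (variance 1 − ρ). There were 200,000 simulated trials per setting. The before-after column shows the runs with ρ = 0.5; those with ρ = 0.8 agree to within 0.2 percentage points.

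| Drift d (SD) | Before-after test significant | Side-difference test significant |
|---|---|---|
| 0 | 4.9% | 4.9% |
| 0.25 | 10.5% | 4.9% |
| 0.5 | 28.2% | 4.9% |
| 0.75 | 54.4% | 4.9–5.0% |
| 1.0 | 78.3% | 4.8–4.9% |
| 1.25 | 92.8% | 4.8% |

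The drift d drops out of treated minus untreated, so the second column does not move.

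**5. What the side comparison costs in power.** The SD of the difference is √(2(1 − ρ)). A true effect of 1 SD becomes 1/√2 = 0.71 at ρ = 0, 1/√1 = 1.00 at ρ = 0.5, and 1/√0.4 = 1.58 at ρ = 0.8. Simulated power is 50%, 78% and 99% respectively, against 78% for before-after without drift.

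**6. Few matched pairs.** The smallest two-sided exact p-value is 2/2^m for m pairs. With m = 5 it is 2/32 = 0.0625, so 0.05 cannot be reached. With m = 6 it is 2/64 = 0.031.

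**The case against.** The strongest reply is that this is a declared open-label pilot. Section 3.1 excludes randomization and crossover, and Section 7.1 claims only this: "The sample size of 10 patients will be sufficient for this pilot study". The lack of a control is a stated choice, and making a side comparison the key result would redesign the study. That stands, and is why the comparison is proposed only as supportive. It does not explain why Section 3.2 seeks equal sides.

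A reader might infer more than the documents support:

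- *That only treated skin is scored.* A Global SCORMA is taken at both visits. It mixes treated and untreated skin, so it is not a control, but it exists.
- *That the plan reserves an untreated side and then ignores it.* Section 3.2 promises only an attempt, when possible, and never says outright that one side stays untreated. Section 5.2 could be read as treating both.
- *That improvement without the cream is to be expected.* Section 4.1 sets no severity threshold, and Section 1.1 does not describe enrolment at a flare. Regression to the mean is possible but not shown. Seasonal change is a weak explanation over two weeks.
- *That the rates above are false-positive rates for the primary endpoint.* They concern the signed rank test. The responder proportion was not simulated.

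It is also fair that an untreated area is an imperfect control. Section 1.1 mentions remote effects of mast cell mediators, although low absorption is expected. If the worse side were chosen for treatment, regression would differ between sides and the 5% figure would fail.

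**Conclusion.** The point holds as a gap between a stated intention and the rest of the plan: the matched-side sentence has no measurement or analysis behind it, and the before-after test cannot separate the cream from change common to both sides. It is worth correcting because the remedy is cheap and the untreated baseline score cannot be reliably recovered later.

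The size is conditional. At a common drift of 0.25 to 1.0 SD, the planned test would be significant in roughly 11% to 78% of trials of an ineffective cream. This rests on normal changes, equal drift and 10 complete matched patients. The documents give no figure for drift, SD or between-side correlation. The finding does not show that such drift will occur, or that the documents require one side to be left untreated.

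**What to change.** 1. Reconcile Section 3.2 with the application instruction in Section 5.2, so that it is clear whether a matched area lies outside the treated area. Which way that is settled is for the investigators.
2. Where such an area exists, add to Sections 3.2, 6.1(a) and 6.5(a) that the same investigator marks it at Visit 1 and records extent and intensity (A and B) for both areas at Weeks 0 and 2. Include pruritus only if it is rated separately for both areas.
3. State a fixed or random rule for which side is treated. A random rule would need a matching line in Section 3.1.
4. In Section 7, add as a supportive analysis the paired treated-minus-untreated change, computed on the same components for both areas, with an estimate, an interval and the number of matched patients. With five or fewer pairs it is descriptive only. State also which SCORMA the existing test uses.
5. If no matched area is to be left outside treatment, delete the matched-side sentence and describe the results as uncontrolled change.

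The cost is one more copy of an existing form per visit, a few minutes of the same investigator's time, and one paired summary. Unmatched patients contribute only before-after data, and power falls if the sides are weakly correlated. The comparison does not remove open-label rating bias, effects of the moisturizing vehicle, or use on the comparison side of the ordinary moisturizers that Section 5.3 permits. It does not apply to SkinDex-16 or to most of component C.
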